### 3 Summary and Rationale

The most important aspects of the humoral (antibody) response against cancer is 1) the ability of antibody to mediated antibody dependent cellular cytotoxicity (ADCC) through CD16, 2) the ability to mediate *in vivo* expansion of the immune population to recruit more killers to generate an anti-cancer response (the IL-15 linker) and 3) recognition of a target antigen (like CD33 being tested here).

[REDACTED]

The Trispecific Killer Engager (TriKE) designated GTB-3550 was designed as a straightforward off-the-shelf product that can be used to treat CD33+ AML/MDS patients in a manner similar to the way rituximab is used to treat B cell malignancies. We believe that a major advantage of our drug as compared to chimeric antigen receptor (CAR) transduced T cells that require cell and gene therapy is the simplicity of our approach.

[REDACTED]

[REDACTED]

The MTD of exogenous IL-15 in humans following continuous IV infusion is 2 ug/kg/day for a total of 10 days (240 hours).

[REDACTED]

## 4 Study Design

This is a multisite Phase I/II clinical trial of GTB-3550 (CD16/IL-15/CD33) tri-specific killer cell engager (TriKE) for the treatment of CD33-expressing high risk myelodysplastic syndromes, refractory/relapsed acute myeloid leukemia or advanced systemic mastocytosis. Up to 10 study centers may take part in this trial.

Patients receive a single course of GTB-3550 TriKE given as 3 weekly treatment blocks. Each block consists of four consecutive 24 hour continuous infusions of GTB-3550 TriKE followed by a 72 hour break after Block #1 and #2. All treatment is given as an inpatient.

Toxicities are monitored through Day 28 (as assessed on Day 29) with continued toxicity assessment through Day 60. Disease response is assessed by bone marrow biopsy performed between Day 21 and 42 after the start of the 1st infusion. Follow-up for response and survival continues through 6 months from study treatment start.

The study consists of two components. The dose finding component is a modified version of a Phase I trial and the extended component is a modified Phase II trial.

**Dose Finding Component:** The Phase I component uses a continual reassessment method (CRM) to determine the maximum tolerated dose (MTD) of GTB-3550 TriKE. Up to 7 doses levels will be tested. The goal of the CRM is to identify the dose level which most closely corresponds to the targeted dose limiting toxicity (DLT) rate of 20%.

Patients are enrolled in cohorts of 2 beginning at Dose Level 1. A minimum of 1 week must separate each patient. Both patients within a cohort must reach Day 28 (end of the DLT assessment period) prior to enrollment of a subsequent cohort. The study statistician assigns each new cohort of 2 patients to the most appropriate dose level based on updated toxicity probabilities. As enrollment proceeds, each cohort is assigned to an increased, decreased or equivalent dose level based on prior data in the trial until the study sample reaches 30. At this time, the last dose is declared the MTD and the GTB-3550 TriKE dose for the extended component.

**Extended Component:** The primary goal of the extended component is to study the potential efficacy of GTB-3550 TriKE in this patient population. Efficacy is measured using rates of complete and partial remission. A Simon's MiniMax two-stage design is used in this phase. Monitoring guidelines are in place to stop the study early for excessive toxicity.

Stage 1 enrolls 13 patients, including all patients treated at the MTD defined during the dose finding component. If 3 or more of these 13 patients have a clinical response to GTB-3550 TriKE, the trial moves to Stage 2 and enrolls an additional 17 patients. If the Phase I component enrolls more than 13 patients at the MTD, the futility rule for the two-stage design will be adjusted with the given number of patients enrolled at the MTD.

If at least 10 of the 30 patients have a clinical response, GTB-3550 TriKE will be considered for further investigation.

Patients experiencing clinical benefit (defined as stable or better) at the time of the 1st disease reassessment may be considered for a 2nd course of GTB-3550 TriKE on a compassionate basis provided they experienced no side effects equivalent to a DLT and continue to meet relevant study inclusion/exclusion criteria. Refer to [Section 7.4](#) for additional information.

## 5 Patient Selection

Study entry is open to adult patients 18 years of age and older regardless of gender, race, or ethnic background. While there will be every effort to seek out and include women and minority patients, the patient population is expected to be no different than that of other high risk malignancies studies at the University Of Minnesota and other participating institutions.

A potential participant must meet all of the inclusion and exclusion criteria to be considered eligible for study participation.

### 5.1 Eligible Diseases

Diagnosis of one of the following CD33-expressing myeloid malignancies with greater than or equal to 50% CD33+ target cells with no good standard of care treatment options including:

High Risk Myelodysplastic Syndromes (MDS) progressive on two or more prior regimens and requiring treatment that meets **at least one** of the following:

- IPSS-R High or Very High Risks
- WHO Classification: RAEB-1 or RAEB-2
- Poor and very-poor risk cytogenetic abnormality as defined by the IPSS-R cytogenetic classifications
- WHO Based Prognostic Scoring System (WPSS): High or Very High Risk

Therapy related MDS and not a candidate for induction chemotherapy or had an inadequate treatment response after induction chemotherapy.

Refractory or Relapsed Acute Myelogenous Leukemia (AML) meeting **at least one** of the following:

- Refractory AML defined as failure to achieve remission after at least 3 induction attempts
  - Elderly AML not fit for induction therapy can be enrolled after 2 failed inductions
- Relapsed AML
  - Not a candidate for hematopoietic stem cell transplant (HSCT), at least one re-induction attempt required
  - Prior HSCT relapse beyond 3 months may be included only if off immunosuppression for a minimum of 4 weeks and do not have GVHD

Notes:

- 1) For hypomethylating agents (i.e. decitabine, azacitidine) to count as an induction/re-induction attempt, the patient must have completed a minimum of 3 monthly cycles
- 2) For targeting agents (i.e. sorafenib) to count as an induction/re-induction attempt, the patient must have completed a minimum of 1 month without attaining CR

Advanced systemic mastocytosis (defined as mast cell leukemia, aggressive systemic mastocytosis, and systemic mastocytosis associated with hematologic neoplasm) may enroll without any prior treatment, given there is no standard established therapy.

## 5.2 Age, Performance Status, Organ Function, Contraception Use

- At least 18 years of age
- Karnofsky score  $\geq 70\%$  ([Appendix I](#))
- Adequate organ function within 14 days (30 days for cardiac and pulmonary) of study enrollment defined as:
  - Renal: an estimated glomerular filtration rate  $\geq 60$  mL/min/1.73 m^2
  - Hepatic: AST, ALT, alkaline phosphatase and total bilirubin within normal range
  - Pulmonary function: DLCO corrected (ml/min/mm Hg) defined as no more than 5 units below lower limit of normal (CTCAE v5 Grade 1 carbon monoxide diffusing capacity decreased) based on patient's height, weight, and gender as reported by the institutional pulmonary function lab.
  - Cardiac: Absence of decompensated congestive heart failure, or uncontrolled arrhythmia; left ventricular ejection fraction  $\geq 45\%$  by echocardiogram, MUGA or cardiac MRI.
- Absolute lymphocyte count (ALC)  $\geq 200$  cells/mm^3 OR absolute circulating CD56+/CD3 NK cell count  $>25$  cells/ $\mu$ l within the 14 days prior to start of therapy
- Sexually active females of childbearing potential and males with partners of child-bearing potential must agree to use adequate birth control during study treatment
- Participant provides voluntary written consent signed before performance of any study-related procedure not part of normal medical care

## 5.3 Exclusion Criteria

- New or progressive pulmonary infiltrates on screening chest x-ray or chest CT scan unless cleared for study by Pulmonary. Infiltrates attributed to infection must be stable/improving with associated clinical improvement after 1 week of appropriate therapy (4 weeks for presumed or documented fungal infections).
- Uncontrolled bacterial, fungal or viral infections, known history of HIV
- Active Hepatitis B or Hepatitis C (virus detectable by PCR) - chronic asymptomatic viral hepatitis is allowed
- Other concurrent active cancer within the last year (excluding non-melanoma skin cancers)
- Severely clinically obese patients, BMI  $>38$

- Currently taking any over-the-counter [OTC], vitamin, mineral, or dietary supplement within 14 days prior to study drug administration on Day 1 and during study conduct that may confound study safety goals (e.g. St. John's wort). Questions should be discussed with GT Biopharma.
- Pregnant or breast feeding. The effect of GTB-3550 TriKE on the fetus is unknown. Females of childbearing potential must have a blood test within 7 days prior to enrollment to rule out pregnancy - must be repeated if not within 7 days of treatment initiation
- History of central nervous system malignancy or symptoms of active CNS disease
- A family history of long QT syndrome or with a QTc interval > 480 msec at screening
- Currently taking medications known to prolong QT/QTc interval as the potential risk of QT/QTc prolongation is unknown in humans (refer to [Appendix V](#) for a list of prohibited medications for eligibility)
- A candidate for potentially curative therapy, including hematopoietic cell transplant
- Unwilling to remain within a 90 minute drive of the study center through at least Day 29

## 6 Patient Screening and Study Enrollment

Written consent must be obtained prior to the performance of any research related tests or procedures. Consent is usually obtained before final eligibility is determined.

### 6.1 Consent and Study Screening in [REDACTED]

Any patient who has been consented is to be entered in [REDACTED] by the Study Coordinator or designee. If a patient is consented but is not enrolled in the study treatment, the patient's record is updated in [REDACTED] as a screen failure and reason for exclusion recorded.

### 6.2 Prior and Concomitant Therapy:

All non-study medications, including prescription, OTC, or herbal therapies, used by the patient will be documented (i) for the 14 days prior to screening (prior medications), (ii) during screening, and (iii) throughout the study (concomitant medications). The Investigator in communication with the Sponsor will review and determine if prior/concomitant medication(s) affect the patient's eligibility to participate or continue to participate in the study.

Administering medications known to elevate Liver Function Tests (LFTs) during the treatment interval and the week before should be avoided. Azole antifungal

agents frequently increase liver function tested in >10% of subjects. For 1 week prior to and concurrent with GTB-3550 administration, patients should be treated with micafungin if medically indicated.

### **6.3 Study Enrollment and GTB-3550 TriKE Dose Level**

To be eligible for this study, the patient must sign the treatment consent and meet each inclusion criteria and none of the exclusion criteria listed on the eligibility checklist based on the eligibility assessment documented in the patient's medical record.

To complete enrollment in [REDACTED], the Study Coordinator or designee records the GTB-3550 TriKE dose level assignment.

### **6.4 Inability to Begin Study Treatment**

If a patient is enrolled to the study, and is later found not able begin the study treatment, for whatever reason, the patient will be taken off study and treated at the physician's discretion. The Study Coordinator or designee will update [REDACTED] of the patient's non-treatment status. The patient will be replaced to fulfill enrollment requirements.

### **6.5 Re-Treatment Enrollment onto 2015LS167R**

Any patient, in the judgement of the Principal Investigator, who experiences lack of disease progression or evidence of clinical improvement after completion of the 1st treatment course may be considered for retreatment per [Section 7.4](#). To be eligible for re-treatment the patient must sign the re-treatment consent and meet each inclusion criteria and none of the exclusion criteria listed on the eligibility checklist based on the eligibility assessment documented in the patient's medical record. Any qualifying patient who has signed the re-treatment consent is entered onto the re-treatment protocol ([REDACTED]) in [REDACTED] by the Study Coordinator or designee.

## **7 Treatment Plan**

In order to provide optimal patient care and to account for individual medical conditions, investigator discretion may be used in the prescribing of all supportive care drug therapy (i.e. acetaminophen, diphenhydramine, G-CSF, antimicrobials, etc.).

### **7.1 GTB-3550 TriKE Administration**

Patients receive a single course of GTB-3550 TriKE at their assigned dose as 3 weekly treatment blocks. Each block consists of four consecutive 24 hour

continuous infusions (over approximately 96 hours) of GTB-3550 TriKE followed by a 72 hour break after Block #1 and #2. All treatment is given as an inpatient.

The assigned dose will be calculated on a weight obtained within 5 days prior to or on day of the 1st dose. The dose is not be recalculated for subsequent treatment blocks.

The institutional Investigational Pharmacy will prepare each 24 hour bag for infusion per [Section 9.6](#) based on the patient's assigned GTB-3550 TriKE dose. Each assigned dose will be administered as a 100 mL infusion over 24 hours period at 4.17 mL/hour rate. Note: actual bag volume is 130 ml to allow for the product sample collection before and after infusion.

**Pre-meds:**

Pre-meds: 30 minutes prior to each infusion, patients will receive acetaminophen 325 mg PO and diphenhydramine 25mg PO/IV. Repeat prn.

**IV Fluid Management:**

IV fluids should be administered at a minimum rate of 50 cc/hour additional fluids given based on the clinical status of the patient.

**Infusion Related Reactions:**

If Grade 2 infusion related reaction occurs, interrupt the infusion and treat symptomatically with antihistamines, NSAIDS, narcotics, IV fluids as medically appropriate. Any patient experiencing a second Grade 2 infusion related reaction after restarting, despite pre-medication or a Grade 3 or 4 infusion related reaction will be permanently discontinued from GTB-3550 TriKE.

Administration of glucocorticoids is prohibited during the TriKE treatment period as the use of systemic steroid medications may result in loss of therapeutic effects of the study drug. They should be avoided except in the event of a severe toxicity.

Any Grade 3 or 4 infusion related reaction will result in permanent discontinuation of study drug with appropriate medical intervention.

**Post-Infusion TriKE Sample Collection (Week 1 infusions only):**

Upon completion of each infusion during Week 1 only, the nursing staff will disconnect the infusion bag and tubing from the patient. Prior to discarding the bag and tubing, two pre-labeled 1.8 ml cryo-vial (containing wording "Post-Infusion" as well as dose and date when bag was prepared) will be filled with a minimum of 1 ml of drug each. This may be done on the unit or the bag/tubing transferred to the institutional research lab and samples collected there. Regardless, the vials or

infusion bag/tubing must be refrigerated while awaiting transfer to the research lab. The research lab will freeze samples for later batch shipping to UMN TTL (if applicable) and testing. Refer to [Section 8.2](#) for additional details.

### **7.1.1 Monitoring Requirements During TriKE Infusions**

#### **Monitoring during the 1st infusion of each continuous infusion (CI) block:**

Vital signs including blood pressure, pulse, temperature, respirations, and pulse oximetry will be measured as follows:

- prior to the infusion start
- every 15 minutes ( $\pm$ 10 minutes) during the 1st hour
- every 30 minutes ( $\pm$ 10 minutes) during the 2nd hour
- every 60 minutes ( $\pm$ 10 minutes) for the next 2 hours
- then every 4 hours ( $\pm$ 20 minutes) for the remainder of the infusion

#### **Monitoring during the infusion 2, 3, and 4 of each CI block:**

Vital signs including blood pressure, pulse, temperature, respirations, and pulse oximetry will be measured as follows:

- every 15 minutes ( $\pm$ 10 minutes) during the 1st hour
- then every 4 hours ( $\pm$ 20 minutes) for the remainder of the infusion

Targeted toxicities ([Appendix VI](#)) and unexpected adverse events will be collected at the time points listed in [Section 10.2](#).

### **7.1.2 Monitoring for Signs of Immune Activation (Phase I Patients):**

In addition to monitoring as above, patients enrolled in Phase I will be monitored for clinical signs of immune activation:

- treatment related tachycardia defined as a heart rate of >30 BPM than baseline heart rate measured each cycle pre-infusion and persists for 4 hours
- fever defined as Grade 2 (>39.0 - 40.0 degrees C [102.3 - 104.0 degrees F]) and persists for 4 hours

If a patient meets either of the above criteria, no dose adjustment will be made unless a dose limiting toxicity (DLT) occurs. Refer to [Section 7.2.1](#) for impact on subsequent dose level escalation.

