**Additional Dose Escalation Parameters (Phase I Only):**

In addition to monitoring for dose limiting toxicity, patients enrolled in the Phase I component will be monitored for signs of immune activation using treatment related tachycardia and fever as clinical markers of transient bioactivity. Refer to [Section 7.1.2](#) Monitoring for Signs of Immune Activation (Phase I patients) for the definition of tachycardia and fever thresholds.

If detected in a single patient (fever or tachycardia lasting > 4 hours OR meets criteria for any DLT) subsequent dose levels will increase by 50% instead of the planned doubling (100% increase). For example, if signs of immune activation occurred at Dose Level 4 (50 µg/kg/day), Dose Level 5 would be adjusted to 75 µg/kg/day rather than 100 µg/kg/day and Dose Level 6 would be 115 µg/kg/day ( $75 \times 1.5$  rounded up to the nearest 5) rather than 200 µg/kg/day.

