## 10 Event Monitoring, Documentation and Reporting

Toxicity and adverse events will be classified according to NCI's Common Terminology Criteria for Adverse Events version 5 (CTCAE v5). A copy of the CTCAE can be downloaded from the CTEP home page at [https://ctep.cancer.gov/protocoldevelopment/electronic\\_applications/docs/CTCAE\\_v5\\_Quick\\_Reference\\_5x7.pdf](https://ctep.cancer.gov/protocoldevelopment/electronic_applications/docs/CTCAE_v5_Quick_Reference_5x7.pdf)

An exception to the use of CTCAE will be for the assessment of cytokine release syndrome (CRS). Individual adverse events which are associated with CRS will be graded per CTCAE; however the ultimate assessment will be made using a revised grading system for CRS as presented by Lee et al.

CRS Revised Grading System (replaces CTCAE v4 CRS grading)	
Grade	Toxicity Description
Grade 1	Symptoms are not life threatening and require symptomatic treatment only, e.g., fever, nausea, fatigue, headache, myalgias, malaise
Grade 2	Symptoms require and respond to moderate intervention - Oxygen requirement < 40% or Hypotension responsive to fluids or low dose of one vasopressor or Grade 2 organ toxicity
Grade 3	Grade 3 Symptoms require and respond to aggressive intervention - Oxygen requirement ≥40% or Hypotension requiring high dose or multiple vasopressors or Grade 3 organ toxicity or grade 4 transaminitis
Grade 4	Life-threatening symptoms - Requirement for ventilator support or Grade 4 organ toxicity (excluding transaminitis)
Grade 5	Death

Grades 2-4 refer to CTCAE v4.0 grading.

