## 10.2 Event Documentation

Event monitoring and documentation begins with the 1st dose of TriKEs.

For the purposes of this study, selected expected adverse events will be assessed using the Targeted Toxicity Worksheet ([Appendix VI](#)) and any unexpected events will be collected at the following time points in relation to the GTB-3550 TriKE infusions through Day 29:

- Prior to the infusion start of each 24 hour infusion (i.e. Day 1, 2, 3, 4, and Day 8, 9, 10, 11, and Day 15, 16, 17, 18)
- At the end of the final infusion of each block (i.e. Day 5, Day 12, Day 19)
- Day 22
- Day 29

At each time point, the worst grade of the targeted toxicity since the last assessment or the previous 24 hours (whichever is shorter) will be recorded in addition to any unexpected toxicities felt at least possibly related the study treatment.

If a patient discontinues study therapy early or otherwise does not receive treatment as planned, the targeted toxicity assessment time points may be adjusted or eliminated; however, patients must be assessed for a minimum of 28 days from the 1st dose of study drug.

If a patient is not abiding by the standard of care study calendar ([Section 8.1](#)), collection of the corresponding targeted events (and research related samples) also may be altered or discontinued on an individual patient basis, as appropriate.

Monitoring for adverse events will end after the last targeted assessment; however, the investigator is obligated, upon knowledge of, to report any event meeting the criteria in [Section 10.5](#).

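### As printed, the fever sign in Section 7.1.2 stops at 40.0 °C, so an isolated Grade 3 fever does not trigger the slower escalation step that a milder Grade 2 fever does (minor; probably a drafting slip)

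*Combined protocol and SAP*

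**What the plan says.** Section 7.1.2 lists two signs for Phase I patients. Tachycardia is a rise of more than 30 beats per minute over the pre-infusion baseline that persists for 4 hours. Fever is "fever defined as Grade 2 (>39.0 - 40.0 degrees C [102.3 - 104.0 degrees F]) and persists for 4 hours".

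Section 7.2.1 (Additional Dose Escalation Parameters) applies them. One patient is enough to trigger the rule, by "fever or tachycardia lasting > 4 hours OR meets criteria for any DLT", and then "subsequent dose levels will increase by 50% instead of the planned doubling (100% increase"). For what counts as fever, that section sends the reader back to 7.1.2 "for the definition of tachycardia and fever thresholds". Its worked example starts from a sign at 50 µg/kg/day and gives 75 and then 115, the latter "rounded up to the nearest 5".

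Three other places decide what happens to a higher fever:

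- **Appendix VI, Fever row:** above 40.0 °C is Grade 3 if it lasts up to 24 hours and Grade 4 if longer. An asterisk on the row points to 7.1.2.
- **DLT definition (Study Schema, 7.2.1, 10.3):** related Grade 4 or 5 non-hematologic events are DLTs. Grade 3 events count only beyond 72 hours, and Grade 3 fever is a named exception.
- **Section 10, revised grading of cytokine release syndrome (CRS):** Grade 1 is "Symptoms are not life threatening and require symptomatic treatment only, e.g., fever, nausea, fatigue, headache, myalgias, malaise".

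**The concern.** The sign is there to slow escalation when a patient shows early clinical evidence of cytokine release. A trigger of that kind should respond at least as readily to a stronger signal as to a weaker one. As printed, the fever sign has a ceiling as well as a floor. No section says *or higher*, and the DLT list does not pick up what falls above the ceiling until the fever becomes Grade 4. A site that follows the text exactly would slow escalation for 39.5 °C and not for 40.4 °C. Up to 10 sites may apply this wording. At stake is the size of the next dose step in a first-in-human escalation.

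**Working it through.** **Step 1. Reproduce the plan's own figure.** The rule is next dose = 1.5 × current dose. From 50: 50 × 1.5 = 75. Then 75 × 1.5 = 112.5, which rounds up to the nearest 5 as 115. Both match the example in 7.2.1.

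**Step 2. Run fevers through the printed rule.** The cases are hypothetical, isolated and treatment-related, each held at one temperature. Grades are from Appendix VI, the fever sign from 7.1.2, and the DLT route from 7.2.1.

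| Fever | Grade | Fever sign as printed | DLT | 50% step as printed | With *Grade 2 or higher* |
|---|---|---|---|---|---|
| 38.8 °C, 6 h | 1 | no | no | no | no |
| 39.5 °C, 6 h | 2 | yes | no | **yes** | yes |
| 40.4 °C, 3 h | 3 | no | no | no | no |
| 40.4 °C, 6 h | 3 | no | no | **no** | yes |
| 40.4 °C, 20 h | 3 | no | no | **no** | yes |
| 40.4 °C, 25 h | 4 | no | yes | **yes** | yes |

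The printed rule is not monotone in severity: Grade 2 triggers, Grade 3 does not, Grade 4 does. The Grade 3 rows miss the DLT route twice over. A Grade 3 fever lasts at most 24 hours by definition, so it cannot exceed 72 hours, and it is also a named exception. The CRS item in the DLT list does not help either, because fever needing only symptomatic treatment is CRS Grade 1. Removing the ceiling changes only the two Grade 3 rows that last longer than 4 hours.

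**Step 3. Size the consequence on the current ladder** (5, 10, 25, 50, 100, 150, 200 µg/kg/day). This assumes that the rounding shown once in 7.2.1 applies to every step.

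| Trigger at | Planned next (increase) | 1.5 × dose, rounded up to 5 | Effect of a trigger |
|---|---|---|---|
| 5 | 10 (+100%) | 7.5 → 10 | none |
| 10 | 25 (+150%) | 15 | lower |
| 25 | 50 (+100%) | 37.5 → 40 | lower |
| 50 | 100 (+100%) | 75 | lower |
| 100 | 150 (+50%) | 150 | none |
| 150 | 200 (+33%) | 225, if the rule applies here | see objection |

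A trigger lowers the next dose in 3 of 6 steps. Without rounding it is 4 of 6, because 7.5 against 10 after the first level then counts too. The Revision History (revision 12) says the next cohort goes from 100 to 150, so the lower steps appear to be past.

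**Step 4. Check the dose-finding model.** The continual reassessment method (CRM) in Section 12.1 updates on DLTs only. The fever sign is not an input, so the estimate of the maximum tolerated dose (MTD) is not touched.

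**The case against.** **Grade 2 was meant as a floor.** Section 7.2.1 calls the values thresholds and puts no ceiling in its own sentence. The Study Schema names fever without a grade, the tachycardia sign is a floor, and the Appendix VI asterisk marks the whole Fever row. This stands as evidence of intent, and is why the point is described as a probable slip. It does not remove the printed upper limit from the only place where the fever sign is defined.

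**Other routes catch the patient.** Tachycardia triggers independently. A fever that climbs above 40.0 °C may spend 4 hours in the band on the way up or down, and another DLT item may apply. The patient is also managed under other rules: CRP, IL-6 and ferritin are assessed for CRS-like symptoms (7.3.6), and a new block needs a temperature of at most 101 °F (7.1.5). All of this stands and narrows the gap, but none of it guarantees the trigger. A reader might go further and infer that a fever peaking above 40.0 °C cannot be caught by time in the band. After the early hours of an infusion, vital signs are taken "then every 4 hours", and on the worksheet "the worst grade of the targeted toxicity since the last assessment or the previous 24 hours (whichever is shorter) will be recorded". The documents do not support that inference. They do not say that persistence must be shown by consecutive in-band readings, temperatures are charted apart from the worksheet, and a Grade 3 entry still sits in the row that points to 7.1.2.

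**No forward dose changes.** After 100 the next dose is 150 with or without a trigger. This stands, and it keeps the point minor.

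**The 225 reading.** A reader might infer that the rule directs 225 instead of 200 after a trigger at 150, which is 225 / 200 = 1.125, or 12.5% higher. The documents do not support that as a finding. The rule replaces a planned doubling, and the step from 150 to 200 is +33%. The ladder ends at 200, and revision 12 gives the aim as more caution than doubling. It is a possible misreading that one sentence would close.

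**Conclusion.** The point holds on the printed text and is minor. By the fever and DLT routes, an isolated fever above 40.0 °C for more than 4 and up to 24 hours does not trigger the 50% step, while a Grade 2 fever and a related Grade 4 fever do. The documents give no basis for how often such a fever would occur without another trigger, so its frequency cannot be estimated.

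Where it would change a dose, the difference is 15 against 25, 40 against 50, or 75 against 100 µg/kg/day. That rests on two assumptions: that the printed rounding applies throughout, and that revision 12 places the trial at 100. Under both, the gap matters mainly if the CRM de-escalates and then re-escalates.

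Two stronger conclusions do not follow. The MTD model is not biased, because it does not use the sign. The difference between 4 hours in 7.1.2 and more than 4 hours in 7.2.1 has no practical weight: it bears only on a sign lasting exactly 4 hours, while the 4-hourly vital signs carry a 20-minute window.

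**What to change.** In Section 7.1.2, define the sign as *fever of Grade 2 or higher (>39.0 degrees C)* with no upper limit, keeping the persistence condition. This is a change to one phrase. It needs no new measurements, because temperature is already charted. The only cost is somewhat slower escalation if the trial re-escalates from 10, 25 or 50 µg/kg/day and such a fever occurs.

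As an optional clarification, add one sentence to Section 7.2.1: after a trigger, the next dose is the lower of a 50% increase and the planned level. The next dose after 150 then stays at 200 on any reading, and the printed example (75, then 115) is unchanged. If both edits are made they should go in together, so that a wider fever trigger cannot be combined with the 225 reading.
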